12.0 STATISTICAL CONSIDERATIONS

12.1 Determination of Sample Size

The sample size is 20 patients with 10 patients in each arm for a 24-week randomized double blind clinical trial. The sample size is justified based on this trial being a proof of concept pilot study. This study will allow us to determine an initial signal for possible efficacy of ABT in Myositis-ILD (Syn-ILD) as well as give safety and tolerability data. Moreover, it will allow us to determine an estimate of the effect size of the study drug and placebo to design a more definitive phase II/III clinical trial. In our cohort about 25% patients with SOC decline by FVC% of $\geq 15\%$ or death or

transplant. Assuming FVC decline by mean of 10% on SOC therapy and trial drug + SOC leads to improvement in FVC% (Even by mean of 5%) we will have >90% power to detect the difference with sample size proposed. Based on our database there is about 25% patients that decline FVC > 10% on SOC for myositis ILD.

12.2 Planned Efficacy Evaluations

12.2.1 Primary Efficacy Variables

The primary end point for statistical analysis will be the percent FVC changes from baseline to week 24 between the 2 treatments arms (SOC/placebo vs. SOC/ABT).

Primary outcome criteria for safety and tolerability will be adverse event (routine adverse events or tolerability issues and serious adverse event) between the 2 treatment arms (SOC/placebo vs. SOC/ABT).

12.2.2 Secondary Efficacy Variables

- a. Time to progression free survival where progression is defined as first occurrence of any of the following: death or lung transplant or FVC $\geq 10\%$ decline *or* FVC $\geq 5\%$ decline with DLCO $\geq 15\%$ decline.
- b. Change in dyspnea, as measured by University of California San Diego Shortness of Breath Questionnaire (UCSD SOBQ) (range 0-120, higher score is worsening dyspnea).
- c. Time to improvement in FVC% by $\geq 10\%$.
- d. Rates of death or requiring lung transplant..
- e. Other individual PFT variables (FEV1%, DLCO%).
- f. Qualitative changes in HRCT chest over 6 months in the two arms using chi-square (or Fischer exact) test. Changes in semi-qualitative scoring of fibrosis over 6 months based on HRCT chest scan images collected from all sites and centrally read by an expert blinded radiologist, will be done as a separately.
- g. Steroid-sparing effect (calculated using prednisone dose equivalents)
- h. Frequency of treatment failures: a) patient meeting worsening criteria or withdrawal due to worsening ILD anytime during the trial or b) FVC% worsening by 10% at 6 months, c) death or transplant within 6 months.

Secondary Outcome Myositis: Given that many patients *may* have concomitant active myositis with muscle and/or skin involvement we will assess clinical outcomes related to both muscle and skin using following secondary outcomes (SOC/placebo vs. SOC/ABT):

Active myositis is defined based on MDAAT at baseline muscle or cutaneous skin disease activity of ≥ 3 on 10 cm visual analogue scale (VAS).

New myositis response criteria and IMACS definition of improvement (DOI) will be used to assess myositis response in drug + SOC vs. placebo + SOC.

12.3 Methods of Analysis

Primary End Point:

The primary end point for statistical analysis will be the percent FVC changes from baseline to week 24 between the 2 treatments arms (SOC/placebo vs. SOC/ABT). Ranked ANCOVA, with average standardized rank change in the predicted FVC% as the outcome measure and the standardized rank baseline as a covariate will be used. Primary outcome criteria for safety and

tolerability will be adverse event (routine adverse events or tolerability issues and serious adverse event) between the 2 treatment arms (SOC/placebo vs. SOC/ABT). Chi-square (or Fischer exact test) and t-test (or Mann-Whitney) will be used based on data variable and distribution. Patients will be stratified for sub-analysis based on their SOC drug

Secondary Analysis (SOC/placebo vs. SOC/ABT) for Syn-ILD:

- a. Time to progression free survival where progression is defined as first occurrence of any of the following: death or lung transplant or $FVC \geq 10\%$ decline *or* $FVC \geq 5\%$ decline with $DLCO \geq 15\%$ decline. This will be done using Cox proportional hazards model and controlling for baseline demographics and $FCV\%$.
- b. Change in dyspnea, as measured by University of California San Diego Shortness of Breath Questionnaire (UCSD SOBQ) (range 0-120, higher score is worsening dyspnea), will be done using Mann-Whitney test.
- c. Time to improvement in $FVC\%$ by $\geq 10\%$. This will be done using Kaplan Meier survival curve and Cox's proportional hazards model after controlling for co-variates.
- d. Rates of death or requiring lung transplant using Chi-square (Fischer exact) test.
- e. Other individual PFT variables (FEV1%, DLCO%) similar to analysis done for primary outcome of $FVC\%$.
- f. Qualitative changes in HRCT chest over 6 months in the two arms using chi-square (or Fischer exact) test. Changes in semi-qualitative scoring of fibrosis over 6 months based on HRCT chest scan images collected from all sites and centrally read by an expert blinded radiologist, will be done as a separately and analyzed using analysis strategy similar to primary outcome.
- g. Steroid-sparing effect (calculated using prednisone dose equivalents) using paired t-test.
- h. Frequency of treatment failures: a) patient meeting worsening criteria or withdrawal due to worsening ILD anytime during the trial or b) $FVC\%$ worsening by 10% at 6 months, c) death or transplant within 6 months. Chi-square test will be used to compare between the two groups.

Secondary Outcome Myositis:

New myositis response criteria (table 1) and IMACS definition of improvement (DOI) will be used to assess myositis response in drug + SOC vs. placebo + SOC.

- a. Comparison of the average Total Improvement Scores during the 6-month treatment period. Repeated measures analysis will be used to compare the two treatment groups and adjustments will be made for the baseline core set measures (CSM) values.
- b. Comparison of the proportion of patient meeting IMACS DOI and time to first IMACS DOI between the 2 arms,
- c. Comparison of the individual CSM in subjects over time between the 2 arms (repeated measures analysis).
- d. Comparison of the magnitude of the effect size between both treatment arms by comparing the proportion of subjects having Total Improvement Scores ≥ 20 (minimal), 40 (moderate) and 60 (major).

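### Section 12.3(a) rests progression-free survival on one ordinary Cox model with unlisted demographics; with few events among 20 patients it is overfitted and may yield no finite hazard ratio

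*Combined protocol and SAP*

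**What the plan says.** Section 12.3(a) defines the endpoint by a composite: "progression is defined as first occurrence of any of the following: death or lung transplant", or an FVC fall of at least 10%, or an FVC fall of at least 5% together with a DLCO fall of at least 15%. On the analysis it says: "This will be done using Cox proportional hazards model and controlling for baseline demographics" and FVC% (printed FCV%). It does not list the demographics, and it names no Kaplan-Meier curve, log-rank or exact test, or rule for sparse events. It sets no time horizon for the endpoint.

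Item (c), time to an FVC improvement of at least 10%, is treated a little differently: "This will be done using Kaplan Meier survival curve and Cox's proportional hazards model after controlling for co-variates". Its covariates are not named.

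Section 12.1 gives the size: "The sample size is 20 patients with 10 patients in each arm". It also states a purpose: "it will allow us to determine an estimate of the effect size of the study drug and placebo", for use in designing a later trial. Its inputs are a cohort rate ("Based on our database there is about 25% patients that decline FVC > 10% on SOC for myositis ILD", with no time window) and mean changes ("Assuming FVC decline by mean of 10% on SOC therapy", against a mean gain of 5% with abatacept). It gives no SD, no abatacept event rate and no event count for progression-free survival.

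**The concern.** Ten patients per arm can produce only a handful of events, and an adjusted Cox model may need more information than that. Two things can go wrong. First, with about as many terms as events, the fitted hazard ratio is unstable, and because the covariates are unlisted they would be chosen after the data are seen. Second, if one arm has no events the partial likelihood has no maximum: the treatment hazard ratio runs to zero or infinity, and the two-sided interval is open at one end.

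Section 12.1 wants effect estimates from this pilot, and the estimate is what an empty arm removes. An empty abatacept arm becomes more likely the better abatacept works. The plan does not say what would then be reported.

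**Working it through.** **The plan's own figure.** The only numeric design figure is power above 90% for a 15-point FVC difference (from -10 to +5) with 10 per arm. For a simple two-sided 0.05 comparison, 90% power needs an SD of at most about 10.3 (normal approximation) or 9.8 (t-test); one-sided, about 11.5 or 11.0. The SD is not stated and the planned test is a ranked ANCOVA, so the claim is attainable but cannot be confirmed. It says nothing about progression-free survival, so event counts have to be derived.

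**Formulas.** With event probabilities pS (standard of care) and pA (abatacept), expected events = 10(pS + pA). The chance that at least one arm is empty is a + b - ab, with a = (1 - pS)^10 and b = (1 - pA)^10.

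**Assumed rates.** The 25% is Section 12.1's, read as a 24-week rate. The 35% and all abatacept rates are assumptions.

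| SOC / ABT event % | Events | a | b | Empty arm |
|---|---|---|---|---|
| 25 / 25 | 5.0 | 0.056 | 0.056 | 11% |
| 25 / 12.5 | 3.75 | 0.056 | 0.263 | 30% |
| 25 / 10 | 3.5 | 0.056 | 0.349 | 39% |
| 35 / 17.5 | 5.25 | 0.013 | 0.146 | 16% |
| 35 / 35 | 7.0 | 0.013 | 0.013 | 3% |

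**Section 12.1's means.** Sections 7.2 and 10.2 schedule PFTs at weeks 12 and 24. Take week-24 means of -10 and +5 from Section 12.1. Assume half of each at week 12, normal changes, equal SD, correlation 0.7, and an event if FVC is down 10 points at either visit.

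| Assumed SD | pS | pA | Events | Empty arm |
|---|---|---|---|---|
| 8 | 54% | 7% | 6.1 | 46% |
| 10 | 55% | 14% | 6.8 | 23% |
| 12 | 56% | 19% | 7.5 | 12% |
| 15 | 57% | 26% | 8.3 | 5% |

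Nearly all of this is an empty abatacept arm. The DLCO limb, death and transplant are not modelled. Each can only add events, so with the other assumptions held these percentages are upper bounds. At SD 10, correlations of 0.5 to 0.9 give 20-29%, and lowering only the week-12 SD to 8 or 7 gives 35% or 41%. If the 10% fall is relative and baseline FVC is assumed to be 60-75%, the threshold is 6-7.5 points; at SD 10 that gives 9.5-8.5 events and 6-11%.

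**Events per term.** Treatment, FVC%, age and sex make four terms; race makes five. The choice of demographics is assumed. The range is 3.5/5 = 0.7 to 9.5/4 = 2.4 events per term.

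**Effect of the covariates.** In 2,000 simulated trials per setting, with those covariates having no true effect, the treatment hazard ratio was not finite in 14-16% (25/25), 32-38% (25/12.5), 44-47% (25/10), 3-5% (35/35) and 22-25% (means, SD 10). The covariates add little to the empty-arm problem; their cost is overfitting and open choice.

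**Check of the remedy.** A Firth-penalised Cox model with treatment and FVC% gave a finite estimate and profile interval in all 300 simulated trials (means, SD 10; 150 each for items (a) and (c)). The median ratio of upper to lower limit was 47 for (a) and 86 for (c). For 3/10 versus 0/10 events, where the ordinary hazard ratio is not finite, it gives about 0.13 (0.001 to 1.4); for 3/10 versus 1/10, about 0.36 (0.03 to 2.4).

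**The case against.** The strongest reply is that this is one secondary endpoint in a 20-patient pilot. Section 12.1 discusses effect size in terms of FVC change, which the primary ranked ANCOVA addresses and which is untouched here. Sections 12.3(d) and 12.3(h) already compare death or transplant and treatment failure by arm without a model. A penalised model also leaves intervals too wide to size a later trial.

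Most of this stands, and it limits the weight of the point. But 12.3(h) is not the same endpoint: it lacks the DLCO limb and counts the 10% FVC fall at six months, not one seen only at week 12. It also gives no time-to-event estimate.

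Stronger readings are tempting, and the documents do not support them:

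- A reader might infer that Section 12.1 implies a definite event count. It does not: its 25% has no time window, and the SD and abatacept rate are absent.
- A reader might infer that the Cox analysis will probably fail. Under the assumptions tabulated, the chance of an empty arm runs from 3% to 46%, so this is a possibility and not a forecast.
- A reader might infer that an empty arm leaves nothing to report. Counts remain, and likelihood-ratio and score p-values can still be computed; what is lost is the point estimate and the two-sided interval.
- A reader might infer that item (c) is equally or more exposed. The documents give no improvement rate, so any percentage there is illustrative only, and Kaplan-Meier is already planned.

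**Conclusion.** The point holds for item (a). An ordinary Cox model with unlisted demographics is the only analysis named, and on any of the assumptions tried it has about 0.7 to 2.4 events per term. That the covariates are open to choice after the data are seen needs no event-rate assumption. The loss of a finite hazard ratio is conditional on an empty arm. Its direction is firm, since an empty abatacept arm is more likely the better the drug works. Its size is not, because it depends on an SD, an abatacept rate, a week-12 mean and a correlation that the documents do not give. For item (c) only the unnamed covariates and the use of an ordinary Cox model carry over.

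This is worth correcting before the data are seen because it is cheap. It does not threaten the primary result.

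**What to change.** Replace the analysis sentence in 12.3(a) with:

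> Progression-free survival over the 24-week randomised phase will be shown by Kaplan-Meier curves by arm, with the week-24 Kaplan-Meier event risk per arm, and compared by an exact (permutation) log-rank test. The hazard ratio will be estimated by a Firth-penalised Cox model with treatment and baseline FVC% only, with a profile-likelihood 95% CI. Event counts and patients censored before week 24 will be listed by arm. If no event occurs in either arm, only counts are reported. Results are descriptive.

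Use the Kaplan-Meier risk, not a risk difference restricted to patients with known week-24 status. That restriction keeps early events but drops early event-free dropouts, and so biases the risk upward.

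In 12.3(c), keep Kaplan-Meier and put the same two-term Firth model in place of the Cox model with unnamed covariates.

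The cost is SAP wording and no new data. Two choices go beyond a fallback and should be made knowingly: demographic adjustment is dropped, and a week-24 horizon is set that the plan does not now state. Intervals stay very wide, so the hazard ratio cannot by itself size a later trial.

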3.1.1 Study Schema

We will enroll 20 adult subjects with Syn-ILD across 5 clinical sites. We expect enrollment to be completed within 15 months. A 1:1 randomization scheme for active drug: placebo as a weekly SQ injection with their SOC for 24 weeks. All patients can then enter an optional open label follow-up after the 24-week randomized, controlled phase, during which all subjects receive 24 weeks of ABT in the same fashion as the initial study phase. This follow-up phase will assess durability, long term response and safety in patients who were in the active treatment arm while allowing the placebo arm to receive active drug, thus improving recruitment and study power.

Patient must have active ILD associated with anti-synthetase syndromes (a subset of myositis) that are being given SOC treatment for ILD. Patients could have refractory disease with flare up or new onset disease. Patient may or may not have active myositis (PM/DM). We anticipate the continued participation of all subjects in open label extension phase.

Open label phase: At the end of the active study period (week 24 closing visit), patients in either arm can enroll into the optional open-label phase of 24-week ABT therapy (125 mg SQ injection weekly).

a. **Standard of Care (SOC):** The SOC of patients with Syn-ILD includes steroids OR another IS agent OR a combination of steroid and another IS agent. Thus, we will allow steroids and/or only 1 additional IS agent. **Additional IS agent can be either mycophenolate mofetil (MMF) or azathioprine (AZA), but not both.** Patients on steroids alone can be enrolled without additional IS agent. Maximum dose allowed for MMF is 3 gms/day and for AZA is 200 mg/day. Patient should be on stable dose of MMF or AZA for 4 weeks and/or stable dose of steroids 2 weeks prior to Visit 1. Visit 1 is the time of first ABT/placebo dosing. Overall goal is to enroll patients into the trial as soon as the SOC drug has achieved stable dosing. Prednisone taper will be allowed at maximum dose of 60 mg at baseline (Visit 1), at which time a forced prednisone taper will commence as outlined below. Dose of concomitant medication cannot change throughout the phase I of the trial (24 weeks) unless safety/toxicity issues supervene.

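### Time to FVC improvement (12.3 item c) has no rule for death or transplant before improvement; if such patients are censored, the Kaplan-Meier curve overstates the proportion who improve

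*Combined protocol and SAP*

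**What the plan says.** Section 12.2.2 lists the endpoint as "Time to improvement in FVC% by $\geq 10" percent, with nothing else in the event definition. For its analysis, section 12.3 item c states: "Time to improvement in $FVC\%$ by $\geq 10\%$. This will be done using Kaplan Meier survival curve and Cox's proportional hazards model after controlling for" unnamed covariates. It gives no censoring rule, no competing-event rule and no cumulative incidence function. It also does not say whether an FVC measured after a lung transplant can count as an improvement.

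Death and transplant do appear in the neighbouring items. Item a counts them as progression and item h as treatment failure. Item d compares them directly: "Rates of death or requiring lung transplant using Chi-square (Fischer exact) test". None of this is carried into item c.

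The only frequency in the documents is in section 12.1: "In our cohort about 25% patients with SOC decline by FVC% of $\geq 15\%$ or death or" transplant. That is a composite with FVC decline, and it has no time horizon.

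The myositis part of 12.3 has a related endpoint in item b: "Comparison of the proportion of patient meeting IMACS DOI and time to first IMACS DOI between the 2 arms". It names no method for the time-to-event part.

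**The concern.** A patient who dies cannot improve later, and after a transplant the FVC no longer describes the diseased lungs. If either event is entered as ordinary censoring, Kaplan-Meier treats that patient as someone who would have gone on to improve at the rate of those still under observation. The resulting 1-KM is then not the proportion of randomized patients who improve, although a reader would take it as that. The same patient would count as progressed in item a, as a failure in item h, and as possibly still improving in item c.

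Section 4.5.3 provides follow-up for at least 24 weeks after study drug is stopped. Stopping treatment therefore need not censor anyone, and apart from study withdrawal and loss to follow-up, death and transplant are the main reasons for early censoring.

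Section 12.1 gives estimation of the drug and placebo effects, for use in designing a later trial, as one aim of this pilot. A biased improvement rate is a poor input to that.

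**Working it through.** **Inputs from the documents.** Section 12.1: "The sample size is 20 patients with 10 patients in each arm"; section 3.1.1 confirms 1:1 allocation. Scheduled lung function tests after baseline in the randomized phase are at weeks 12 and 24 (7.2, 10.2, Appendix B). The assumed mean FVC changes are -10 on SOC and +5 on ABT plus SOC (12.1). Item c has no stated figure to reproduce; the power of more than 90% in 12.1 belongs to the primary comparison and does not enter here.

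**Assumed, because not stated.** The 24-week risk q of death or transplant, taken over 0 to 25%; the SD of FVC change; the improvement rates.

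**Step 1: exact 10-patient arms.** Let d1 patients be lost before week 12 and d2 between weeks 12 and 24. Let k1 improve at week 12 and k2 at week 24.

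- Proportion who improve = (k1+k2)/10
- At risk at week 12: r1 = 10-d1. At risk at week 24: r2 = 10-d1-k1-d2
- With losses censored, 1-KM = 1-(1-k1/r1)(1-k2/r2)

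If all losses precede week 12 (d2 = 0, d = d1), this reduces to (k1+k2)/(10-d). The overstatement factor is 10/(10-d): 10/9 = 1.11 for d = 1 and 10/8 = 1.25 for d = 2.

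| d1 | k1 | d2 | k2 | Improved | 1-KM |
|---|---|---|---|---|---|
| 0 | 2 | 0 | 2 | 40% | 1-(8/10)(6/8) = 40.0% |
| 0 | 2 | 1 | 2 | 40% | 1-(8/10)(5/7) = 42.9% |
| 1 | 2 | 0 | 2 | 40% | 1-(7/9)(5/7) = 44.4% |
| 2 | 2 | 0 | 2 | 40% | 1-(6/8)(4/6) = 50.0% |
| 1 | 2 | 1 | 1 | 30% | 1-(7/9)(5/6) = 35.2% |
| 0 | 1 | 2 | 2 | 30% | 1-(9/10)(5/7) = 35.7% |
| 2 | 1 | 0 | 1 | 20% | 1-(7/8)(6/7) = 25.0% |
| 1 | 3 | 0 | 3 | 60% | 1-(6/9)(3/6) = 66.7% |
| 0 | 2 | 2 | 0 | 20% | 1-(8/10)(5/5 unchanged) = 20.0% |

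The last row has losses but no later improvement, and hence no bias. Comparing the 20% row that has two early losses with the 60% row that has one, the overstatement is 5.0 points against 6.7.

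**Step 2: expected size.** Spread q and a Kaplan-Meier improvement probability p evenly over the two intervals: per-interval loss is 1-√(1-q) and per-interval improvement is h = 1-√(1-p). Then cumulative incidence = √(1-q)·h + (1-q)(1-h)·h. For p = 40% and q = 10%: 0.9487×0.2254 + 0.9×0.7746×0.2254 = 0.2138 + 0.1571 = 0.371, an overstatement of 2.9 points. The same formula gives 0 at q = 0, 1.4 at 5% and 7.4 at 25%.

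**Step 3: which arm is affected more.** Take the plan's means, an assumed SD of 10 and normality. The chance of a gain of at least 10 is 1-Φ(20/10) = 2.3% on placebo and 1-Φ(5/10) = 30.9% on ABT. With q = 25% on placebo and 5% on ABT, the overstatement is 0.4 points on placebo and 1.1 on ABT, so it is larger in the arm with fewer deaths. Other SDs (placebo against ABT): SD 8, 0.1 against 1.0; SD 12, 0.9 against 1.2; SD 15, 1.7 against 1.3. In relative terms the placebo arm is affected more: a factor of 1.24 against 1.04 at SD 10.

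**Step 4: how likely it is to arise.** The chance of at least one death or transplant among 20 patients is 1-(1-q)^20: 18% at q = 1%, 64% at 5%, 88% at 10%. If half the risk falls before week 12, the chance of two or more early losses in an arm of 10 is about 2.5% at q = 5%, 9% at 10% and 36% at 25%.

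**The case against.** The strongest reply is that Kaplan-Meier does not force the bias. No censoring rule is written, and an analyst could keep patients who die or are transplanted at risk as non-improvers to week 24. With no other early censoring, the Kaplan-Meier curve would then equal the cumulative incidence. That stands: a reader might infer that the plan must censor these patients, and the documents do not say so. What remains is that censoring is the ordinary default and that the plan leaves the choice open.

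Second, the events may be few or absent. Section 4.2 excludes patients listed for transplant, those with FVC or FEV1 at or below 30%, those with high resting oxygen needs and those with end-stage fibrosis. The 25% in 12.1 cannot be split. This also stands, and it makes the size conditional.

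Third, a reader might infer that the arm with more deaths always gains most, or that the order of the arms could reverse. Step 3 does not support the first as a general rule in percentage points. A reversal such as 4/10 = 40% on ABT against 3/7 = 42.9% on placebo needs three early placebo losses. That is above the 2.5 per 10 implied even if the whole 25% composite were death or transplant within 24 weeks. It also needs 30% of placebo patients to improve, against 2.3% under the plan's means at SD 10. With two early losses placebo would read 3/8 = 37.5%, a shift of 7.5 points. The standard error of the 4/10 against 3/10 difference is √(0.4×0.6/10 + 0.3×0.7/10), about 21 points.

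Fourth, a Cox model with censoring at death still estimates a cause-specific hazard ratio. Preferring a Gray test or a Fine-Gray model to it is a choice of estimand, not the correction of an error. Finally, death and transplant enter items a, d and h, so they are not hidden from the reader.

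**Conclusion.** The concern holds in a limited form. Item c names Kaplan-Meier for an event that death and transplant can preclude, and gives no rule for them. If they are censored, 1-KM is never below the proportion who improve, and is above it once such a loss precedes a later improvement in the same arm. With 10 per arm the factor is 1.11 for one loss before week 12 and 1.25 for two; with none it is 1. On average, at a Kaplan-Meier estimate of 40%, the excess runs from 0 to 7.4 points for an assumed 24-week risk of 0 to 25%.

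These figures rest on assessment at weeks 12 and 24 only, and on assumed death, transplant and improvement rates. The documents do not support a statement that the result will be overstated, or that one arm will be favoured. The matter is minor: one secondary endpoint in a 20-patient pilot, where sampling error is much larger than this bias.

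**What to change.** Add to 12.3 item c, before unblinding, wording to this effect:

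> Death and lung transplant before improvement are competing events. Such patients are counted as non-improvers to week 24, and no FVC measured after transplant counts as improvement. The cumulative incidence of improvement is reported by arm in place of 1-KM. The Cox hazard ratio is reported as cause-specific.

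If patients are also lost to follow-up, the Aalen-Johansen estimator handles both kinds of incomplete observation.

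Apply the same rule for death to time to first IMACS DOI in the myositis part of 12.3, and name the method there. That endpoint concerns only patients with active myositis at baseline.

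The cost is a little SAP wording and a small programming change, with no new data. The stated improvement rate will be slightly lower than 1-KM in an arm where a death or transplant precedes a later improvement.

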2.2 Secondary

The secondary objectives include assessing: (a) radiographic improvement, (b) improvement in other PFT variables like FEV1 and DLCO, (c) time to improve in composite outcome for ILD by OMERACT, (d) death/transplant, (d) patient-reported outcomes of dyspnea, (e) rapidity and magnitude of response to ABT, (d) steroid-sparing effect of ABT, (e) durability of response, and (f) assessment of drug effect on other muscle or skin manifestations using standard myositis response criteria.

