3.3.2 Secondary Outcome Measures

(SOC/placebo vs. SOC/ABT) for Syn-ILD:

- a. Time to progression free survival where progression is defined as the first occurrence of any of the following: death or lung transplant or FVC $\geq 10\%$ decline *or* FVC $\geq 5\%$ decline with DLCO $\geq 15\%$ decline.
- b. Change in dyspnea, as measured by University of California San Diego Shortness of Breath Questionnaire (UCSD SOBQ) (range 0-120, higher score is worsening dyspnea).
- c. Time to improvement in FVC% by $\geq 10\%$.
- d. Rates of death or requiring lung transplant.
- e. Other individual PFT variables (FEV1%, DLCO%)
- f. Qualitative changes in HRCT chest over 6 and 12 months in the two arms. Changes in semi-qualitative scoring of fibrosis over 6 months based on HRCT chest scan images collected from all sites and centrally read by an expert blinded radiologist, will be done as a separately and analyzed.
- g. Steroid-sparing effect (calculated using prednisone dose equivalents)
- h. Frequency of treatment failures: a) patient meeting worsening criteria or withdrawal due to worsening ILD anytime during the trial or b) FVC% worsening by 10% at 6 months, c) death or transplant within 6 months.
- i. Quantitative changes in mean Six minute walk distance (6MWD)

j. Quantitative changes in mean daily step count on Fitbit One®.

Secondary outcome criteria for myositis: Myositis response will be evaluated among patients with concomitant active myositis. Active myositis is defined based on MDAAT at baseline muscle or cutaneous skin disease activity of ≥ 3 on 10 cm visual analogue scale (VAS).

New myositis response criteria (table 1) and International Myositis Assessment & Clinical Studies Group (IMACS) definition of improvement (DOI) (given below) will be used to assess myositis response in drug + SOC vs. placebo + SOC.

IMACS DOI: 3 of 6 core set measures (CSM) improved by $\geq 20\%$, with no more than 2 CSM worsening by $\geq 25\%$ (a worsening measure cannot be the manual muscle testing (MMT)).

Table 1. New Myositis Response criteria (based on conjoint analysis continuous definition using absolute % change in six core set measures)

1000Minds Model (absolute % change)		Improvement score for each level of CSM
Core Set Measure		
MD Global Absolute % Change		
Up to $\leq 5\%$		0
$>5\%$ up to $\leq 15\%$		7.5
$>15\%$ up to $\leq 25\%$		15
$>25\%$ up to $\leq 40\%$		17.5
$>40\%$		20
Patient Global/Parent Global Absolute % Change		
Up to $\leq 5\%$		0

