10.2 Evaluations During Treatment

- PFT (FVC, FEV1, diffusing capacity of the lungs for carbon monoxide (DLCO)) will be evaluated at baseline (accepted if within prior 1 month of screening visit), 3, 6 months (+/- 2 weeks). If patient opts into the open label phase, then additional PFT at 12 months will be done.
- HRCT chest at baseline i.e. visit 0/1 (accepted within 3 months of screening visit if no significant change in clinical status has occurred in 3 months) will be done as standard of care (SOC) in clinical practice. HRCT chest at 6 month (+/- 1 month) follow up i.e visit 3 will be done as SOC as well. In patients opting for open label phase, additional HRCT at 12 months (+/- 1 month) follow up i.e visit 5 will be collected if done as SOC.

- Muscle enzyme: creatine kinase (CK) and aldolase levels at baseline, 3, 6 months. If open label phase – then additional 9 and 12 months will be obtained.
- Safety monitoring labs – complete blood count (CBC), liver function test (LFT), serum creatinine will be done at baseline, 3 and 6 months. If patient opts for open label phase, these safety labs will also be done at 9 and 12 months.
- Research specimens (serum, cells, etc) collected at each study visit for future experimental studies.

Refer to study schema in Appendix B

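### Qualitative HRCT change serves a directional objective but is compared by chi-square or Fisher, and its levels are undefined; with three ordered levels, an ordered test would usually detect a consistent shift better

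*Combined protocol and SAP*

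**What the plan says.** The objective is set in section 2.2: "The secondary objectives include assessing: (a) radiographic improvement". Section 3.3.2 f lists the outcome as "Qualitative changes in HRCT chest over 6 and 12 months in the two arms" and names no levels. The test appears in 12.2.2 f and 12.3 f: "Qualitative changes in HRCT chest over 6 months in the two arms using chi-square (or Fischer exact) test". Neither place names a trend, rank or ordinal test.

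The same item in 12.3 has a second HRCT measure, a fibrosis score from a blinded central reading. That one is to be "analyzed using analysis strategy similar to primary outcome", which means ranked ANCOVA, a method that uses order.

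An HRCT ILD assessment form is named in section 7.1 and Appendix B, but its content is not in the text. On numbers, section 12.1 says "The sample size is 20 patients with 10 patients in each arm". On scans, section 10.2 says "HRCT chest at 6 month (+/- 1 month) follow up i.e visit 3 will be done as SOC as well", so HRCT depends on routine care.

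**The concern.** A change variable that serves an improvement objective has a good end and a bad end. Elsewhere the protocol describes HRCT change in the other direction: worsening is part of the definition of active ILD (3.1.1) and of the ILD worsening criteria (4.5.2). Improved, unchanged, worse is therefore the natural set of levels.

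A general chi-square or Fisher test on such a table asks only whether the two distributions differ in any way. This has two consequences:

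- With three levels it spends 2 degrees of freedom, and it can miss a steady shift toward improvement that a test directed at the shift would detect.
- It can be significant for a pattern with no net benefit. With assumed improved/unchanged/worse rates of 10/80/10 on placebo and 45/10/45 on abatacept, equally many more patients improve and worsen. At 10 per arm chi-square is then significant 88% of the time and Wilcoxon 9%.

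Because the levels are not written down, both the categories and any collapsing of them stay open until the data are seen.

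**Working it through.** **No HRCT figure to reproduce.** The only stated power is for FVC% (12.1: "we will have >90% power to detect the difference with sample size proposed"). It gives no standard deviation and does not bear on HRCT. No HRCT rates, effect size or power are given, so every rate below is an assumption.

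**Inputs.** 10 per arm (12.1); three ordered levels (assumed); two-sided 5% (assumed).

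**One table by hand.** Placebo 1/4/5, abatacept 5/4/1 (improved/unchanged/worse). Column totals are 6, 8, 6, so the expected counts per arm are 3, 4, 3.

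- Chi-square = 4 × (2²/3) = 5.33 on 2 df; p = exp(−5.33/2) = 0.069. Fisher (Freeman-Halton) p = 0.064.
- Wilcoxon: the midranks for worse, unchanged and improved are 3.5, 10.5 and 17.5. The abatacept rank sum is 5×17.5 + 4×10.5 + 1×3.5 = 133, against 10×21/2 = 105 expected. The tie-corrected variance is [100/(20×19)] × (6×7² + 8×0² + 6×7²) = 154.7. So z = 28/12.44 = 2.25 and p = 0.024. The exact Wilcoxon p is 0.044.

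**Power by full enumeration.** Each arm has 66 possible tables (12×11/2), giving 66² = 4,356 pairs. Power is the sum of the multinomial probabilities of the pairs with p ≤ 0.05.

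| Placebo vs abatacept (improved/unchanged/worse, %) | Chi-square → Wilcoxon, tie-corrected | Gain | Fisher → exact Wilcoxon | Gain |
|---|---|---|---|---|
| 20/50/30 vs 40/45/15 | 13.0 → 18.2 | 5.2 | 11.4 → 13.3 | 1.9 |
| 15/50/35 vs 40/50/10 | 24.5 → 34.7 | 10.2 | 22.1 → 26.9 | 4.8 |
| 10/50/40 vs 50/40/10 | 47.2 → 59.4 | 12.2 | 43.5 → 51.2 | 7.7 |
| 5/45/50 vs 45/45/10 | 61.0 → 73.8 | 12.8 | 57.1 → 65.6 | 8.5 |
| 20/45/35 vs 67/27/6 | 50.0 → 63.9 | 13.9 | 47.6 → 55.3 | 7.7 |

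The last row is a proportional-odds shift with odds ratio 8. The odds of improved are 0.25×8 = 2, giving 67%; the odds of worse are (35/65)/8 = 0.067, giving 6%.

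**Type I error** under 30/40/30 in both arms: chi-square 4.7%, tie-corrected Wilcoxon 4.7%, Fisher 3.9%, exact Wilcoxon 3.1%.

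**Collapsing to two levels.** For 10/50/40 vs 50/40/10, Fisher power is 29.5% for improved vs not and 15.2% for worse vs not. Both are below the three-level Fisher test (43.5%).

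**Where the ordered test does worse:**

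- Unchanged becomes improved only (10/60/30 vs 50/20/30): chi-square 48.8%, Wilcoxon 21.7%; exact versions 45.1% and 20.0%.
- Worse becomes unchanged only (10/50/40 vs 10/85/5): 37.2% and 31.5%; exact 34.4% and 24.5%.

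**Fewer evaluable scans.** For 10/50/40 vs 50/40/10:

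- 8 per arm: 36.6 → 49.3 (exact 29.9 → 38.6).
- 6 per arm: 31.1 → 36.5 (exact 15.9 → 23.8). At this size chi-square has a type I error of 6.3% under 30/40/30, so its power there is flattered.

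**The case against.** The strongest objection is that the three levels are not in the documents. Section 12.3 gives chi-square tests to the plainly binary items d and h as well, so item f may also be binary. With two levels no order is ignored and there is nothing to gain. This stands, and it makes the finding conditional. It also shows that the levels need defining.

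Second, a reader might infer a fixed power loss of roughly 9 to 13 points. The documents do not support that. They give no HRCT rates, and that range depends on large-sample tests and moderate to large shifts. A small shift gains 5.2 points, or 1.9 with exact tests. With 3 to 4 patients expected per cell, Fisher may well be the test used, so the exact column matters.

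Third, the ordered test is not always better. In the two adjacent-level patterns above no patient does worse, yet it loses 27.1 and 5.7 points (48.8 − 21.7 and 37.2 − 31.5). The first of these is radiographic improvement in its simplest form. This stands, and the plan should say so.

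Fourth, the plan is not blind to order on HRCT, since the fibrosis score is analysed by ranks. That lowers the stakes but does not settle the point: the score covers fibrosis, while the qualitative item is not so limited.

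**Conclusion.** The point holds in a conditional form. The plan names a test that ignores direction for a directional objective and leaves the levels undefined. If there are three ordered levels and abatacept shifts patients consistently toward improvement, an ordered test at 10 per arm gains about 5 to 14 points of power (large-sample) or about 2 to 9 (exact). Collapsing to two levels loses more in the main scenario. The gain is nil for a two-level variable and negative when patients move only between adjacent levels or when both extremes grow.

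A reader might also infer that the stated test is invalid. It is not: at 10 per arm its type I error stays below 5% under the null examined. This is a matter of efficiency and of matching the test to the objective.

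All rates are assumed, and evaluable numbers may fall below 10 per arm because scans come from routine care. Priority is low: this is one of many secondary outcomes in a 20-patient pilot, with no decision rule attached to HRCT.

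**What to change.** In 12.2.2 f and 12.3 f, before unblinding:

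- Record qualitative HRCT change as improved, unchanged or worse.
- Compare the arms with one pre-specified ordered test, the Wilcoxon rank-sum test. State whether the tie-corrected or the exact version is used. It replaces the general chi-square/Fisher test for this item.
- Report the counts per level in each arm, so that patterns the ordered test handles poorly remain visible.
- State that the test has less power when patients move only between adjacent levels or when both extremes increase.

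The cost is a sentence or two of SAP wording, with no new patients, scans or readers. If the assessment form turns out to record only two levels, one field on it would need a third option. The price in power is the one named in the last bullet.
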